After Cycle 1 and Cycle 2, which will only occur if needed, of usability testing are complete, we will email all study participants a link to the final NDR tool. If Cycle 3 is needed, participants will run through the NDR tool independently and then fill out an online survey hosted on REDCap. This survey will include a modified version of the USE Scale (a measure of usefulness, satisfaction, ease of use, and ease of learning) to measure the participant's final satisfaction with the tool. Additionally, we will ask participants to complete a brief, semi-structured interview over the phone to assess the overall NDR tool's acceptability, satisfaction, and overall impressions. This semi-structured interview will help enhance the quantitative data collected in Cycle 3.

Aim 2: All study timepoints will take place online (REDCap survey) with the exception of the study screener (phone) and e-CONSENT (participant will view online while research study coordinator is on the phone).

Baseline Survey 1: Participants who consent to participate in the study will be sent a link to the REDCap Baseline Survey 1 to their email address. The Research Study Coordinator will confirm that the Baseline Survey 1 link was received while they are still on the call with the participant after the e-Consent to ensure it was sent to the correct email address, was not in a Spam/Junk folder, etc. Participants will have 7 days to submit their completed Baseline Survey 1.

Anticipated participant time required to complete Survey 1: 35 minutes

Study Intervention - Assigned NDR Exercises: Once the completed Baseline Survey 1 is received from the study participant, the Research Study Coordinator will send them a unique study link which includes their embedded randomization assignment (pre-randomized) to their email. The link will give participants access to the study website, www.NegotiAge.com, as well as the negotiation platform where they will access their assigned NDR exercises, IAGO. Participants will have 14 days to complete their assigned exercises.

Anticipated participant time required to complete Study Intervention – Assigned NDR Exercises*: 10-30 minutes

*Participants will be randomized to which/how many negotiation activities they are required to do so we are providing a range of time.

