Table 1: Full Factorial Design

Experimental Condition	NDR Exercises by Relationship Conflict Content			
	Caregiver - Patient – Easy [Constant]	Caregiver-Caregiver	Caregiver-Physician	Caregiver - Patient – Difficult
1	Yes	No	No	No
2	Yes	No	No	Yes
3	Yes	No	Yes	No
4	Yes	No	Yes	Yes
5	Yes	Yes	No	No
6	Yes	Yes	No	Yes
7	Yes	Yes	Yes	No
8	Yes	Yes	Yes	Yes

Table 2: Study Components, Time-Points

Intervention		Follow-Up Surveys		
Baseline Survey (T1)	Intervention Completion	Post-NDR Survey (T2)	1 Month (T3)	3 Month (T4)

including themes of spirituality, meaning, mastery, and control, which provided the most important issues facing caregivers. The extensive care needs of individuals with AD are variable, and care typically involves great demands on spouses and other family members.¹¹⁹⁻¹²¹ By examining the wellbeing of the family caregiver as a primary outcome, we will be able to detect how the demands and care needs of their loved ones are affected by the interventions. In addition, among family caregivers of people with AD, there are high rates of anxiety, stress, and depression.^{122,123} Research has shown that poor caregiver mental health was associated with increased patient mortality, even after controlling for sex, age, dementia severity, and patient mental health.¹²⁴ Family caregivers experience anxiety when advocating for their loved ones health care needs.¹²⁵ NDR training may minimize anxiety. Thus, we will measure secondary outcomes of 1.) Anxiety (Patient-Reported Outcomes Measurement Information System (PROMIS) - Anxiety) and Neuro-QoL Caregiver-specific Anxiety¹²⁶ 2.) Caregiver Stress (Caregiver Stress Index), 3.) Caregiver Burden (Zarit Family Caregiver Burden Scale)¹²⁷ 4.) Fatigue (PROMIS)¹²⁸, 5.) Self-Efficacy as measured by PROMIS General Self-Efficacy and Caregiving Self-efficacy scales¹²⁹⁻¹³¹ and 6.) Received Support as measured by PROMIS Emotional/Informational Support, and Social Roles.

Table 3: Process and Patient-Centered Outcome Measures

Constructs	Measurement	Months		
		0	1	3
Patient Centered Outcomes				
Well-Being	(Primary outcome) Neuro-QOL – Positive Affect and Well-Being – Short Form	X	X	X
Anxiety	*PROMIS Ca Adult Item Bank Emotional distress-Anxiety; NEURO-QoL Caregiver Specific Anxiety	X	X	X
Satisfaction with Social Roles	PROMIS Ca Satisfaction with social roles/activities	X	X	X
Caregiver Burden	Zarit Family Caregiver Burden Scale	X	X	X
Fatigue	PROMIS Ca Fatigue	X	X	X

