Data Collection. We will utilize REDCap Surveys software for data entry.¹³² REDCap is a secure, encrypted, Web-based application designed to support data capture for research studies, providing 1) an intuitive interface for validated data

entry; 2) audit trails for tracking data manipulation and export procedures; and 3) automated export procedures for seamless data downloads to common statistical packages. This software allows for straightforward electronic entry of responses and can generate output data files compatible with statistical programs. Drs. [name] and [name] will oversee the database structure and quality assurance activities.

Data Analysis: Power Calculation. The goal of this research is to inform a RCT trial of an optimized intervention. We will achieve that goal by evaluating feasibility and generating effect sizes of each component on changes in outcomes. The effect sizes will inform which components to retain in the optimized intervention and be used to power a subsequent trial. The pilot trial is not powered for hypothesis testing; however, a power calculation was run to determine the effect size this pilot trial will be powered to detect. With 120 subjects total and 40 subjects in each component group, we will be able to detect effect sizes of 0.65 with 80% power using a two-sided t-test at a type I error rate of 5%. For the primary outcome of Neuro-QOL Positive Affect and Well-Being, this equates to a mean difference of 3.9, assuming a standard deviation of 6. Calculations employed Rochon's GEE method, as implemented in SAS GEESIZE v. 3.1 macro implemented by Dahmen.¹³³⁻¹³⁶

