Data Analyses: Aims 2 and 3 Quantitative. Data will be stored on a HIPAA-compliant server with secure access for approved study staff. Analyses will be conducted using SAS 9.4. For **Aim 2a**, we will calculate averages of acceptability ratings, number of exercises completed (retention to treatment), and prescribed strategies documented (compliance). These data will be used to derive expected usage rates for a future trial. For **Aim 2b**, we will assess the effect of each component on changes in Neuro-QOL – Positive Affect and Well-Being across time (baseline-1 month post-intervention), which will be done by comparing combinations of participants across conditions. Analyses will be conducted using intent-to-treat linear mixed effects models, accounting for data collected at multiple assessment time points nested within individual participants. For each component, we will test differences in change in outcomes across time, with baseline values as the reference. Thus, the effects will be modeled as component x time interactions. Cohen's *d* will be calculated by dividing the mixed effects model derived intervention effect estimate by the pooled standard deviation of the outcome. We will also report results disaggregated by sex and test sex as a moderator to evaluate sex differences in outcomes, which will inform the need for any sex-specific approaches in an optimized intervention. For **Aim 3**, exploratory analyses using linear mixed models will be performed to test two-way interactions between components on changes in weight and binge eating (e.g., Component 1 x Component 2 x time). Interaction tests are to determine if a set of components impact the overall effect and thus should be retained together in the optimized intervention.

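### Component effects are planned as change from baseline without using the equal baseline means that randomization provides; a common-baseline model would narrow the intervals with no new data

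*SAP*

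**What the plan says.** The SAP, under Data Analyses: Aims 2 and 3 Quantitative, sets the model class: "Analyses will be conducted using intent-to-treat linear mixed effects models, accounting for data collected at multiple assessment time points nested within individual participants". The Aim 2b contrast is then defined: "For each component, we will test differences in change in outcomes across time, with baseline values as the reference". The next sentence gives the model term: "Thus, the effects will be modeled as component x time interactions". The main window is baseline to 1 month. SAP Table 3 and the instrument table in Protocol section 7.0 agree that Positive Affect and Well-Being is measured at baseline, 1 month and 3 months.

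The SAP does not say whether a component main effect is fitted, whether time is categorical, or which covariance structure is used. It names no baseline covariate and no constraint on the baseline means.

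On timing, Protocol section 7.0 (Aim 2, assigned exercises) says: "Once the completed Baseline Survey 1 is received from the study participant, the Research Study Coordinator will send them a unique study link". That link carries an assignment from a list generated in advance.

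**The concern.** In the usual model (component, time, component x time), each level of a component has its own freely estimated baseline mean. With complete data and categorical time, the baseline to 1-month interaction then equals the difference in mean change scores. The baseline survey is returned before the assignment is released, so the assignment cannot affect it, and under randomization the true baseline means are the same at both levels of every component. Estimating two means that are known to be equal adds variance and removes no bias.

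Precision matters more here than in many pilots. The SAP's power paragraph says that the trial is not powered for hypothesis tests. Its product is an effect size per component, used to choose components and to power the next trial.

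**Working it through.** **Inputs.**
- SD 6, mean difference 3.9, 40 per component group, 80% power, two-sided 5%: SAP, Power Calculation.
- Group size per component: in SAP Table 1 each component is on in 4 of 8 conditions. With equal cells, 120 participants give 120 x 4/8 = 60 v 60 (15 per cell).
- Correlation r between baseline and 1-month scores: not in the documents; 0.3 to 0.9 is assumed.
- Follow-up: the SAP cites more than 90%, so 10% missing serves as a sensitivity case.

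**The plan's own figure.** The SAP states: "With 120 subjects total and 40 subjects in each component group, we will be able to detect effect sizes of 0.65 with 80% power". 3.9/6 = 0.65. A two-sided t-test with 40 v 40 has power 0.819 at d = 0.65, so the figure reproduces. At the 60 v 60 that Table 1 implies, the same test detects d = 0.516, or 0.516 x 6 = 3.1 points. The points-scale results below use 60 v 60, with 40 v 40 shown for comparison.

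**Formulas**, with n per level and s the SD of the score:
- Change contrast (free baseline means): variance = 2(1 - r) s² (2/n).
- Common baseline mean: variance = (1 - r²) s² (2/n).
- Variance ratio = (1 - r²) / [2(1 - r)] = (1 + r)/2. Interval-width ratio = square root of (1 + r)/2.
- Number of participants that 120 is worth = 120 x 2/(1 + r).

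**Worked case, r = 0.5, n = 60, s = 6.** s times the square root of 2/60 is 1.095. Change: SE = 1.095 x √1.00 = 1.095, half-width 1.96 x 1.095 = 2.15. Common mean: SE = 1.095 x √0.75 = 0.949, half-width 1.86. In units of d this is 2.15/6 = 0.36 against 1.86/6 = 0.31.

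| r | SE, change | SE, common mean | Half-width, change | Half-width, common mean | Narrower by | 120 is worth |
|---|---|---|---|---|---|---|
| 0.3 | 1.296 | 1.045 | 2.54 | 2.05 | 19% | 185 |
| 0.5 | 1.095 | 0.949 | 2.15 | 1.86 | 13% | 160 |
| 0.7 | 0.849 | 0.782 | 1.66 | 1.53 | 8% | 141 |
| 0.8 | 0.693 | 0.657 | 1.36 | 1.29 | 5% | 133 |
| 0.9 | 0.490 | 0.477 | 0.96 | 0.94 | 2.5% | 126 |

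At 40 v 40 the half-widths are 2.63 to 2.28 (r = 0.5), 2.04 to 1.88 (r = 0.7) and 1.66 to 1.58 (r = 0.8). The percentages do not change.

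**Checks.** Generalized least squares for the 2x2x2 design with months 0, 1 and 3 gives the same 1-month ratios. With 10% missing at each follow-up, the width ratios are 0.876, 0.93, 0.95 and 0.98 at r = 0.5, 0.7, 0.8 and 0.9, against 0.866, 0.922, 0.949 and 0.975 with complete data. A simulation of 120 participants (4,000 runs per r), which pays for estimating the baseline slope, gives mean half-widths of 2.16 to 1.88, 1.67 to 1.55 and 1.37 to 1.31 at r = 0.5, 0.7 and 0.8.

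**Two consequences.** When r is below 0.5, 2(1 - r) exceeds 1, so the change contrast is less precise than ignoring baseline altogether. Also, the change contrast subtracts a chance baseline difference in full, although only a fraction r of it is expected to persist at follow-up. A one-SE difference (1.1 points) therefore moves the estimate by (1 - r) x 1.1, or 0.55 points at r = 0.5, in the opposite direction. Over repeated randomizations this averages to zero.

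**The case against.** The strongest reply is that the SAP does not commit to the less precise model. A common-baseline model is also a component x time model that measures change from baseline; it merely omits the component main effect. This stands. The documents show a model that is not fully specified, and the loss arises only on the usual reading. But two analysts could follow the paragraph and report different estimates and interval widths, so the SAP should choose.

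The second reply is that the gain rests on an unknown r. This stands too: at r = 0.8 the half-width falls by only 0.07 points, and at r = 0.9 by about 0.02.

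Third, the SAP does not say whether SD 6 refers to the score or to change. If it refers to change, the planned half-width at 60 v 60 is 2.15 at every r, and at r = 0.8 it would fall to 2.15 x 0.949 = 2.04. The percentages hold either way; the points do not.

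A reader might infer more than the documents support:
- That baseline data are discarded. They are not: baseline is an outcome in the model and the reference for each contrast. What goes unused is the equality of the baseline means.
- That the planned analysis is biased or its intervals invalid. Neither follows; this is a matter of efficiency.
- That baseline is collected before assignment. The list is pre-randomized, so baseline precedes the release of the assignment. That is enough to justify a common mean.

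**Conclusion.** The point holds as one of efficiency and specification. Aim 2b does not use the equal baseline means that randomization provides. If a component main effect is fitted, the estimates are unbiased but less precise than the same data allow. The 1-month interval could be about 19% narrower at r = 0.3, falling to 5% at r = 0.8 and 2.5% at r = 0.9. A claim that the gain is clearly large would go too far without a value for r.

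This rests on equal allocation to the eight conditions, similar variance at baseline and 1 month, and analysis of everyone randomized, as the SAP's intent-to-treat wording implies. A common baseline mean would not be justified by design in a set restricted to completers. To first order, the alternative is no less precise at any r below 1. It is a free improvement, not the repair of an error.

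**What to change.** In the SAP's Aim 2b paragraph, specify one mixed model with all three components, categorical time, unstructured covariance and component x post-baseline-time terms, with no component main effect at baseline (a constrained longitudinal model). In practice the component indicators are set to zero in the baseline rows. Report each component effect with its 95% interval.

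If a covariate-adjusted model is preferred, regress the follow-up scores on the components, time, component x time, baseline and baseline x time. The last term is needed because there are two follow-ups: without it a single baseline slope is forced on months 1 and 3, and the model no longer corresponds to the constrained one. The two also treat incomplete follow-up differently, so name one as primary before the outcome data are analysed by assignment.

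The cost is a paragraph of SAP wording and a small change to the SAS code. No new data are needed.

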STUDY PROTOCOL

Version Date: 2/22/24

NCT04837937

STUDY TITLE: Negotiation Training to Optimize Caregiver Communication in Alzheimer's Disease

PRINCIPAL INVESTIGATOR:

[name], MPH, MBA

Geriatrics

CO-INVESTIGATORS:

[name]

Preventive Medicine (Biostatistics)

[name]

Preventive Medicine (Behavioral Medicine)

VERSION DATE:

02/22/24

RELATED STUDIES:

N/A

Funding Agency:	National Institute on Aging (NIH/NIA)	
Sponsored Research ID#:	5R01AG068421-03	
Does the grant indicate that covered activities will include Human Research? (Yes / No / Unknown)	Yes	
	Institution	Human Research Assessment *** (e.g., Non-Exempt Human Research, Exempt Human Research, Not Human Research, etc.)
Prime Award Recipient*	Northwestern University Feinberg School of Medicine	Human Research
Sub-Award Recipients**	N/A	N/A

1.0 Purpose and rationale of the study:

The purpose of this study is to design a Negotiation and Dispute Resolution training intervention to improve communication and address resolution of conflicts that family caregivers of patients with Alzheimer's Disease (AD) or memory loss frequently experience.

Specific aims:

Aim 1: Employ a caregiver (user)-centered design approach to modify and tailor negotiations and dispute resolution (NDR) training intervention to support communication skills of family caregivers of adults with AD.

Aim 2: Utilizing Multiphase Optimization Strategy (MOST), conduct a randomized trial of the NDR intervention that targets better communication between caregivers and health teams, using a 2³ full factorial design, to (2a) determine the feasibility of delivering the intervention, and (2b) derive estimates of the effect of 3 intervention components on changes in patient-centered outcomes at post-intervention and follow-up.

Exploratory Aim 3: Explore if intervention components (lectures/exercises) interact to change communication between caregivers and health care teams at post-intervention and follow-up.

2.0 Enrollment Criteria (who can be in your study and who would not be eligible to participate in your study):

No subjects will be excluded on the basis of race or ethnicity.

In **Aim 1**, participants will be eligible if they:

1. Are age 21 or older;
2. Speak and read English (NDR is currently not available in other languages);
3. Provide caregiving support (e.g. emotional, social, physical, task-related) to an older adult (>age 65) at least one hour per week;

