Survey Time Points. Subjects will be asked baseline questions by phone prior to initiation of the intervention. After the NDR training is complete, subjects will automatically be provided an electronic survey. Subjects will then be contacted at 1 and 3 months (+/- 2 weeks) through their email to completed follow-up surveys electronically (Table 2). We chose time-points of 1 month to gain information on the NDR training and 3 months for sufficient time for caregivers to utilize the information presented in the NDR training and detect changes in outcomes.

Assessments. During the initial assessment, research staff will collect baseline variables that map to the Conceptual Model of Negotiation, specifically to Contextual Factors of the Negotiator and Structural. These include:

Demographics. information on the caregivers subject (e.g. gender, education, work experiences) as well as proxy demographics of the care recipient with AD.

Intervention-Centered Outcomes. We will assess feasibility of the NDR training with caregivers through assessments of a) Study Recruitment Rates (# of people), b) Study Retention Rates (# of people), c) Completion of NDR Training Exercises and d) Acceptability (System Usability Scale [a 10-item measure of usability]^{105,106} and the USE Scale [a 30-item measure of usefulness, satisfaction, ease of use, and ease of learning]).¹⁰⁷ A multiple choice questionnaire will be conducted to ascertain knowledge of negotiation strategies. After the intervention and in follow-up months, participants will complete a brief, semi-structured interview to assess perception of the assigned intervention program, satisfaction, and progress, with both Likert scales and open-ended questions to obtain qualitative data.

Patient-Centered Outcomes. As this proposal seeks to tailor and test a novel NDR intervention to improve the lives of family caregivers, the primary outcome will be Positive Affect and Well-being. The Positive Affect and Well-Being (Neuro-QOL PAW)¹¹⁸ measure was designed to aid clinicians and researchers to better evaluate and understand the potential role of positive health processes for individuals and has been previously validated. This choice was supported as its development emphasized the importance of early qualitative input from neurology professionals, patients, and caregivers. In development of the Neuro-QOL, interview and focus group participants spontaneously reported positive responses to chronic illness,

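### The SAP's only quantitative analysis for exploratory Aim 3 names outcomes that this trial does not collect (weight and binge eating), so it cannot be run as written

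*SAP*

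**What the plan says.** Both documents state Aim 3 in the same terms. Protocol Section 1.0 reads: "Explore if intervention components (lectures/exercises) interact to change communication between caregivers and health care teams at post-intervention and follow-up".

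The analysis is in the SAP under Data Analyses: Aims 2 and 3 Quantitative. For Aim 3, "exploratory analyses using linear mixed models will be performed to test two-way interactions between components on changes in weight and binge eating", using a component-by-component-by-time term in a linear mixed model. The SAP then gives the purpose: "Interaction tests are to determine if a set of components impact the overall effect and thus should be retained together in the optimized intervention".

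The same paragraph describes the Aim 2b analysis of Neuro-QOL Positive Affect and Well-Being. There, "we will test differences in change in outcomes across time, with baseline values as the reference", and the stated window is baseline to 1 month after the intervention.

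The SAP's Power Calculation paragraph sets the context. "The effect sizes will inform which components to retain in the optimized intervention", and "The pilot trial is not powered for hypothesis testing".

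**The concern.** The aim and its analysis name different outcomes, and the analysis names two that do not belong to this trial. An analyst following the SAP literally would have no data to put into the Aim 3 model.

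Two things are at stake. An aim stated in both documents has no quantitative analysis that can be carried out. The interaction tests are also meant to inform which components stay together in the optimized intervention, and as written they cannot. If the outcome is filled in only at analysis, the choice of measure and time contrast could be made with the results in view.

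**Working it through.** No arithmetic is needed for the main point, and the plan gives no figure for Aim 3 to reproduce. The check compares the named outcomes with what is collected.

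**Step 1. Are the named outcomes collected?**

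| Place | Measures listed | Weight | Binge eating |
|---|---|---|---|
| SAP, Assessments text and Table 3 | Demographics, well-being, anxiety, stress, burden, fatigue, self-efficacy, support and social roles, feasibility and acceptability, DUTCH, negotiation knowledge and utilization, program assessment | no | no |
| Protocol Section 7.0, instruments by time-point | The survey instruments, including sociodemographics, PANAS and the IAGO post-assessment | no | no |

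Protocol Section 4.0 says that Aim 2 data come from online survey questions, and no weighing is described. Outcomes named for Aim 3 that are collected: 0 of 2.

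**Step 2. Does another passage supply an Aim 3 analysis?** The SAP's Research Design paragraph mentions testing interactions between exercises but names no outcome or model. The qualitative paragraph describes thematic coding and tests no interactions. No replacement is given.

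**Step 3. Which interactions are affected?** SAP Table 1 varies three components; the easy caregiver-patient exercise is constant. Two-way interactions: 3 choose 2 = 3. All three are affected.

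**Step 4. What could fill the gap?** SAP Table 3 has one row whose label includes communication, Negotiation Processes/Communication, with three measures. The Aim 3 sentence speaks of changes, so a measure needs a value before the intervention. The protocol schedule gives:

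| Measure | Survey 1 | Survey 2 | Survey 3 | Survey 4 |
|---|---|---|---|---|
| DUTCH | yes | yes | yes | yes |
| Negotiation Knowledge | yes | yes | yes | yes |
| Negotiation Utilization | no | yes | yes | yes |

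Measures with a baseline: 2 of 3. This count rests on the protocol schedule. The month-0 column of SAP Table 3 is not secure evidence of a pre-intervention value, because it also marks USE/SUS and completion of the exercises. Neither can precede training, and the protocol places USE and SUS at Survey 2 only.

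**Step 5. Is the time frame given?** Largely. The aim covers post-intervention and follow-up, and SAP Table 2 defines T2, T3 and T4. What is missing is the contrast over those surveys for Aim 3; the only window stated in the analysis paragraph belongs to Aim 2b.

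**Step 6. How much choice is left open?** Counting one score per measure: 2 measures with a baseline x 3 interactions x 3 post-baseline surveys = 18 candidate contrasts.

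**The case against.** The strongest reply is that this is a stray phrase in one exploratory sentence. The aim itself names communication, Table 3 has a single row for that construct, the surveys are defined, and the model form is given. No recruitment, randomisation or data collection depends on the phrase. Most of this stands, and it is why the point is moderate. It does not supply the missing content: the row holds three unranked measures, one without a baseline, and no contrast is stated.

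A reader might infer more than the documents support:

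- **That the intended outcome cannot be recovered at all.** The construct can be; the specific measure and contrast cannot.
- **That none of the three measures captures communication with health care teams, so Aim 3 cannot be answered.** The documents are only silent on this. The SAP says of knowledge that "A multiple choice questionnaire will be conducted to ascertain knowledge of negotiation strategies", but the items of the three measures are not reproduced and their content cannot be judged here. It is a separate question of construct validity, which would remain if the SAP had named DUTCH.
- **That a formal retention rule has failed.** The SAP states a purpose for the interaction tests, with no threshold or algorithm.
- **That Aim 3 must have one main outcome.** For an exploratory aim in a pilot that is a preference. Naming and reporting all eligible measures also cures the defect.

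**Conclusion.** The point holds. Neither of the two outcomes named for Aim 3 is collected, so the analysis cannot be run as written for any of the three two-way interactions, and their stated use in informing which components are retained together has no usable outcome.

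The severity is moderate: it should be fixed. A reader might take an impossible analysis as a threat to the trial's main result, but the documents do not support that. Aim 3 is exploratory, the SAP disclaims power for hypothesis testing, and the primary outcome and Aim 2b are specified separately and are unaffected.

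The conclusion assumes that the listed measures are complete, and in particular that the sociodemographic survey, whose items are not set out in full, does not record body weight as an outcome. It also takes the protocol schedule as the authority on which measures have a baseline.

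**What to change.** Amend the Aim 3 sentence in the SAP's quantitative analysis section:

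1. Replace weight and binge eating with the named outcome or outcomes from the Negotiation Processes/Communication row that have a Survey 1 value in the protocol schedule: DUTCH (stating which score), Negotiation Knowledge, or both.
2. State the contrast over Surveys 2, 3 and 4 relative to Survey 1.
3. List the three interactions, each by time: Caregiver-Caregiver x Caregiver-Physician; Caregiver-Caregiver x Caregiver-Patient Difficult; Caregiver-Physician x Caregiver-Patient Difficult.
4. Report all named measures.
5. If Negotiation Utilization is included, compare it between conditions after baseline and not as a change, since it starts at Survey 2.
6. If outcome data have already been examined, say so, date the change and label the Aim 3 results post hoc.

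The cost is SAP wording only. The data are already scheduled, and the model form can stay as it is.
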